13.3. APPENDIX 3 - COMMON TERMINOLOGY CRITERIA FOR ADVERSE EVENTS (CTCAE) VERSION 5.0

The CTCAE version 5.0 can be accessed via the following link:

https://ctep.cancer.gov/protocolDevelopment/electronic_applications/docs/CTCAE_v5_Quick_Reference_8.5x11.pdf

1 LIST OF ABBREVIATIONS AND DEFINITIONS OF TERMS

Abbreviation	Definition
ADR	Adverse Drug Reaction
AE	Adverse Event
AESI	Adverse Event of Special Interest
ATC	Anatomic Therapeutic Chemical
BMI	Body Mass Index
BP	Blood Pressure
BT	Body Temperature
CI	Confidence Interval
CP	Conditional Power
CRF	Case Report Form
CTCAE	Common Terminology Criteria for Adverse Events
DB	Data Base
ENR	Enrolled Analysis Set
EOS	End of Study
ETDV	Early Trial Discontinuation Visit
FAS	Full Analysis Set
FDA	Food and Drug Administration
GCP	Good Clinical Practice
ICH	International Conference on Harmonisation
IP/IMP	Investigational Product/ Investigational Medicinal Product
MedDRA	Medical Dictionary for Regulatory Activities
NA	Not Applicable
NEWS	National Early Warning Score
PCR	Polymerase Chain Reaction
PD	Protocol Deviation
PI	Principal Investigator
PP	Per Protocol
PR	Pulse Rate
PT	Preferred Term
QC	Quality Control
RTF	Rich Text Format
SAE	Serious Adverse Event
SAF	Safety Analysis Set
SAP	Statistical Analysis Plan
SD	Standard Deviation
SOC	System Organ Class
SpO2	Oxygen Saturation
TEAE	Treatment Emergent Adverse Event
TESAE	Treatment Emergent Serious Adverse Event
TLF	Tables Listings Figures
WHODD	World Health Organization Drug Dictionary

2 INTRODUCTION

This document describes the rules and conventions to be used in the presentation and analysis of efficacy and safety data for Protocol RLX0120. It describes the data to be derived, summarized and the statistical analyses to be performed.

This Statistical Analysis Plan (SAP) is based on study protocol version 3.0, dated 22 Dec 2020.

3 STUDY OBJECTIVES AND ENDPOINTS

3.1 STUDY OBJECTIVES

The objective of this study is to evaluate the efficacy and safety of two different doses of raloxifene orally administered compared to placebo in patients with early diagnosis of paucisymptomatic COVID-19

3.1.1 PRIMARY OBJECTIVES

- Evaluation of the effectiveness of therapy in reducing the proportion of patients who still have viruses in the upper airways after 7 days of therapy.
- Evaluation of the effectiveness of therapy in reducing the proportion of patients who requires supplemental oxygen therapy and/or mechanical ventilation within 14 days of starting therapy.

3.1.2 SECONDARY OBJECTIVES

- Evaluation of the effectiveness of therapy in reducing the proportion of patients who still have viruses in the upper airways after 14 and 28 days of therapy.
- Evaluation of the effectiveness of therapy in reducing the proportion of patients who requires supplemental oxygen therapy and/or mechanical ventilation within 7 or 28 days of starting therapy.
- 7, 14 and 28 days drug safety and tolerability profile.
- Assessment of body temperature, blood and biochemical parameters between T0 and T28.

3.2 STUDY ENDPOINTS

3.2.1 PRIMARY ENDPOINTS

- Virologic outcome - Proportion of patients with undetectable SARS-CoV-2 at PCR at day 7 after randomization.
- Clinical outcome - Proportion of patients who does not require supplemental oxygen therapy (NEWS ≤2) and/or mechanical ventilation at day 14 after randomization.

3.2.2 SECONDARY ENDPOINTS

- Proportion of patients with undetectable SARS-CoV-2 at PCR at day 14 after randomization at day 28 after randomization.
- Proportion of patients who does not require supplemental oxygen therapy

(NEWS ≤2) and/or mechanical ventilation at day 7 and 28 after randomization.

- Proportion of patients in each NEWS category at time 7, 14 and 28 after randomization.
- Mean value of NEWS category at time 7, 14 and 28 after randomization.
- Proportion of patients with any adverse event with grade ≤ 2 according to CTCAE at day 7, 14 and 28 after randomization.
- Proportion of patients with any severe adverse events (grade ≥ 3 according to CTCAE) at day 7, 14 and 28 after randomization.
- Proportion of hospitalized patients who at the beginning of the study were at domicile isolation at day 7, 14 and 28 after randomization.
- Proportion of patients admitted to intensive care at day 7, 14 and 28 after randomization.
- Proportion of survivors at day 7, 14 and 28 after randomization.
- Mean variation of value of the following biomarker parameters, from baseline to day 7, 14, 21 and 28 after randomization:
 - Complete blood cell counts.
 - Hepatic function (ALT, AST and bilirubin).
 - Coagulation (PT, aPTT and INR).
 - Other marker including (D-dimer, CPK, LDH).
- Quality of life questionnaire 3 months after the randomization.

4 STUDY DESIGN AND SCHEDULE OF EVENTS

4.1 STUDY DESIGN

4.1.1 DESCRIPTION OF THE STUDY

This is a Multicenter, adaptive, double blind, randomized, placebo controlled, parallel group, to study efficacy and safety, with the following adaptive components:

- Parallel multi-arms (2 interventional arms and 1 placebo control arm).
- A 2-stage sequential design (1 interim analysis + 1 final analysis).
- Sample size re-calculation at interim stage.
- Stopping rule for efficacy or futility at interim stage.

4.1.2 SAMPLE SIZE

The sample size of the study has been based on the following assumptions:

- Virologic assumption: Early treatment with antivirals increases the proportion of patients with undetectable SARS-CoV-2 in upper respiratory tract at day 7 after therapy from 25% to 50%.
- Clinical assumption: Early treatment with antivirals increases the proportion of

patients who recover without need of mechanical ventilation and/or supplemental oxygen therapy by the day 14 after therapy from 50% to 75%.

Based on these assumptions and considering a randomization ratio 1:1:1, the sample size will be adaptively determined to achieve a power greater than 80% to show superiority of raloxifene vs placebo in terms of either one of primary endpoint and controlling the one-sided alpha below 0.025.

Sample size will be determined through the following steps:

- an interim analysis will take place when 50 patients per arm (N=150) have reached their primary endpoints (i.e. assessments available).
 - In case of efficacy of at least one treatment arm or futility of both arms (see criteria in protocol section 9.3) the study enrollment will be stopped,
 - otherwise the actual number of new patients in each arm may be blindly reassessed according to observed efficacy of the best favourable and promising arm;
- in case of continuation of the study to the final stage, it is expected to randomize on average additional 174 patients, depending on sample size reassessment and possible dropping of an ineffective treatment arm. Expected sample size will be between 250 and 450 randomized patients;
- drop-outs of randomized subjects will not be replaced.

This approach allows either to minimize the number of enrolled patients if the experimental assumptions are too conservative or to have a good power level if they are too optimistic.

Pocock's spending functions and conditional power (CP) will be used to control the type I and II errors, considering that interim analysis will be performed when half of the initial planned patients have been reached the primary endpoints (i.e. assessments available).

Bonferroni method is used to adjust for multiple endpoint vs treatment comparisons. Sample size calculation has been performed through simulation (100000 replications). The statistical software used for simulation was SAS®, Version 9.4.

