4.3 INTERIM ANALYSIS

An interim analysis was planned for this study when half (i.e 50 participants per arm (N=150)) of the planned evaluable patients would have reached the primary endpoints at 7 and 14 days (i.e., assessments available).

The intent of the interim analysis was either for identification of early superiority of raloxifene (early efficacy), or for an early stop of one or both treatment arms for futility, or for blind sample size reassessment.

Due to the premature interruption of the enrolment (with 68 patients included in the study), no interim analysis will be done.

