In the SAS® procedure PROC GENMOD, a Type III analysis will be performed by adding the model options: TYPE3, DIST=BIN and LINK=LOGIT.

If the model does not converge then the following steps will be performed subsequently:

- PROC GENMOD with EXACT statement will be used.
- If the model still does not converge, then remove the factors/covariates from the model one by one (according to statistical significance) until convergence reached.
- If the model still does not converge, then perform the Fisher's exact using the SAS procedure PROC FREQ without adjusting for any pre-defined factor and covariates.

The following hypotheses will be tested:

- The null hypothesis for the virologic endpoint is that proportion of treated patients with undetectable SARS-CoV-2 at PCR at day 7 after randomization ($\pi_{RALOXIFENE}$) is lower or equal the placebo one ($\pi_{PLACEBO}$). Two sets of null and alternative hypotheses are provided, one for each treatment dosage:

$$H_{01-60mg}: \pi_{RALOXIFENE-60mg} \leq \pi_{PLACEBO}$$

$$H_{11-60mg}: \pi_{RALOXIFENE-60mg} > \pi_{PLACEBO}$$

$$H_{01-120mg}: \pi_{RALOXIFENE-120mg} \leq \pi_{PLACEBO}$$

$$H_{11-120mg}: \pi_{RALOXIFENE-120mg} > \pi_{PLACEBO}$$

- The null hypothesis for the clinical endpoint is that proportion of treated patients who does not require supplemental oxygen therapy (NEWS ≤ 2) and/or mechanical ventilation at day 14 after randomization ($T_{RALOXIFENE}$) is lower or equal the placebo one ($T_{PLACEBO}$). Two sets of null and alternative hypotheses are provided, one for each treatment dosage:

$$H_{02-60mg}: T_{RALOXIFENE-60mg} \leq T_{PLACEBO}$$

$$H_{12-60mg}: T_{RALOXIFENE-60mg} > T_{PLACEBO}$$

$$H_{02-120mg}: T_{RALOXIFENE-120mg} \leq T_{PLACEBO}$$

$$H_{12-120mg}: T_{RALOXIFENE-120mg} > T_{PLACEBO}$$

Superiority of raloxifene will be established if at least one null hypothesis is rejected.

The frequency and percent will be presented by treatment and visit for both primary endpoints results.

The following figures will be produced for both primary endpoints results:

- Bar chart for Proportion of Patients with undetectable SARS-CoV-2 at PCR by treatment and visit
- Bar chart for Proportion of Patients who does not require supplemental oxygen therapy (NEWS ≤ 2) and/or mechanical ventilation by treatment and visit

The following listings will be presented:

- Listing for the Nasopharyngeal Swab Test (PCR) results
- Listing for the supplemental oxygen therapy (NEWS ≤ 2) and/or mechanical ventilation

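### The SAP keeps the >80% power and 250-450 patient adaptive plan as live text although enrolment stopped at 68, where power is about 13-25% per comparison and 37-59% for any rejection.

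*SAP*

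**What the plan says.** SAP 4.1.2 carries over protocol 9.1. It assumes that treatment raises viral clearance at day 7 from 25% to 50%, and the share free of oxygen or ventilation need by day 14 from 50% to 75%. With 1:1:1 allocation, "the sample size will be adaptively determined to achieve a power greater than 80% to show superiority of raloxifene vs placebo" on either primary endpoint, "controlling the one-sided alpha below 0.025". The interim falls at 50 per arm, an average of 174 further patients is expected, and the total lies between 250 and 450. Multiplicity is covered by one sentence: "Bonferroni method is used to adjust for multiple endpoint vs treatment comparisons".

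SAP 4.3 then states: "Due to the premature interruption of the enrolment (with 68 patients included in the study), no interim analysis will be done". SAP 18(d) repeats that the interim is dropped because enrolment was interrupted. It says nothing about power, sample size or the final critical value.

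The decision rule in SAP 14.1.1 is unchanged: "Superiority of raloxifene will be established if at least one null hypothesis is rejected". The same section specifies logistic regression on observed data with Wald tests.

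**The concern.** SAP 4.3 was rewritten in the past tense once enrolment had stopped, while 4.1.1 and 4.1.2 still describe a design to be carried out. The only power figure in the SAP is therefore one that the trial cannot deliver, and nothing marks it as superseded.

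What is at stake is how a non-significant result will be read. Against a stated power above 80%, it looks like a fairly reliable negative. With about 23 patients per arm, non-rejection is the likely outcome for any given dose and endpoint even if raloxifene works exactly as the plan assumes.

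**Working it through.** **Inputs.** Rates 25% vs 50% and 50% vs 75%, one-sided 0.025 overall, 1:1:1 allocation, 50 per arm at interim (SAP 4.1.2); efficacy bound 2.69640 at both looks (protocol 9.3, Table 1); 68 patients (SAP 4.3).

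**Critical values.** Two doses × two endpoints give four comparisons, so 0.025/4 = 0.00625 one-sided each, z = 2.498. The documents do not write out this split, but the bound confirms it: solving P(Z1 > c or Z2 > c) = 0.00625 for two looks at 50% and 100% information (correlation √0.5) gives c = 2.6964. With no interim, the single final test could use either 2.498 or 2.6964, and the SAP does not say which. Both are shown.

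**Power formula per comparison.** With n per arm and difference 0.25:
- SE1 = √[(0.25×0.75 + 0.50×0.50)/n] = √(0.4375/n), unpooled
- SE0 = √(2×0.375×0.625/n) = √(0.46875/n), pooled
- power = Φ[(0.25 − c×SE)/SE1], where SE is SE1 (unpooled) or SE0 (pooled)

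The 50% vs 75% endpoint has the same variances, so it gives the same values.

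**Planned design first.** The interim at 50 per arm is described as half, so n = 100. SE1 = 0.0661 and SE0 = 0.0685. At 2.6964:
- unpooled: Φ(3.780 − 2.696) = 86%
- pooled: Φ[(0.25 − 0.1846)/0.0661] = 84%

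Two-look simulation (100,000 runs, no reassessment or futility stop) gives 85% at 100 per arm and 88% at 108 per arm ((150 + 174)/3 = 108). Power for at least one of four exceeds 99%. The plan's >80% therefore reproduces. The 174 and the 450 cannot be checked, because the reassessment rule and cap are not given.

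**At 68.** n = 68/3 = 22.7, SE1 = 0.1389, SE0 = 0.1438.
- c = 2.498: unpooled Φ(1.799 − 2.498) = 24%; pooled Φ[(0.25 − 0.3592)/0.1389] = 22%
- c = 2.6964: unpooled Φ(1.799 − 2.696) = 18%; pooled Φ[(0.25 − 0.3878)/0.1389] = 16%

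Simulation of all four tests with a shared placebo arm, all 68 evaluable, both doses effective on both endpoints, latent endpoint correlation 0 to 0.5:

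| Test | Critical value | Per comparison | At least one of four |
|---|---|---|---|
| Two-proportion Z | 2.498 | 21-25% | 53-59% |
| Two-proportion Z | 2.6964 | 16% | 41-45% |
| Unadjusted Wald | 2.498 | 17-20% | 46-50% |
| Unadjusted Wald | 2.6964 | 13-15% | 37-40% |

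The Wald rows take 22 on placebo and 23 on each dose. If the arm of 22 is a raloxifene arm, the last row falls slightly, to 12-15% and 36-37% (correlation 0-0.3).

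**Sensitivity.**
- Only one dose works (Z): any-rejection power about 25-41%.
- Only the virologic effect is real (Z): 36% at 2.498, 26% at 2.6964.
- Fisher's exact test at 0.00625, the SAP's last fallback: 35-42%.
- Bonferroni over the two doses only (0.0125 each, one reading of SAP 14.1.1): about 31% per comparison and 62-71% for any rejection (Z).
- Any-rejection power passes 80% only with no multiplicity adjustment and nearly independent endpoints (83%).

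**Size needed.** Unpooled, n = (c + 0.8416)² × 0.4375/0.0625. This gives 3.339² × 7 = 78.1, so 79 per arm, at 2.498, and 3.538² × 7 = 87.6, so 88, at 2.6964. Pooled variance gives 83 and 93. The range is 79-93 per arm.

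**Detectable effects with 80% power at 22.7 per arm.** From 25%: to 69-73% at 2.498, or 71-76% at 2.6964. From 50%: to 91-93%, or 92-95%.

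**Precision.** The unadjusted 95% half-width for a difference at the assumed rates is 1.96 × 0.1389 = 0.27. An observed 25-point gain would have an interval of about −2 to +52 points.

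**The case against.** The strongest reply is that the SAP contains no wrong calculation. Section 4.1.2 sits under study design, opens by saying what the sample size was based on, and repeats the protocol; for the planned size its claim is correct. The early stop is disclosed in 4.3 and again in 18(d), so an attentive reader sees 68 against 250-450. Low power does not bias the estimates or invalidate the tests, and the planned 95% confidence intervals will show the imprecision. All of this stands.

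Two stronger readings are tempting, and the documents do not support them. One is that the SAP claims more than 80% power for 68 patients; it nowhere says so. The other is that keeping the at-least-one rejection rule after an early stop is itself an error; with Bonferroni over the four comparisons it still controls type I error.

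The achieved-power figures also need care. The SAP specifies Wald tests with center, age, status, their treatment interactions and, for the clinical endpoint, baseline NEWS. The Z figures are therefore optimistic, and even the Wald figures ignore covariates. The 68 are described only as included, and missing results are not imputed, so fewer may be evaluable.

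What the reply does not answer is that the power statement remains live text, no replacement is given, and section 18 is silent on it.

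**Conclusion.** The point holds as a failure to update and report, not as an error in the original sample size. The stated >80% applied to a trial that will not take place. For the trial being analysed, each dose-endpoint test would miss the assumed effect about 75-87% of the time (100 minus 25 to 13), and the trial as a whole would reject nothing in about 41-63% of cases (100 minus 59 to 37).

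This rests on 22-23 evaluable patients per arm, the plan's own rates true for both doses and both endpoints, latent endpoint correlation of 0-0.5, and a critical value of 2.498 or 2.6964. Missing data, or an effect in one dose only, would lower the figures. A looser Bonferroni split would raise them, but not to 80%.

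**What to change.** Keep the original rationale, but label SAP 4.1.1-4.1.2 as the original plan, now superseded. Then add:

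1. The number enrolled (68), and approximate power per comparison and for at least one rejection, or expected confidence interval width, with the assumptions shown and figures matched to the planned Wald test.
2. The critical value that applies at the single final analysis.
3. A sentence that non-rejection will not be read as absence of effect.
4. An entry in section 18 and matching text in the study report.

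Do not add a pooled raloxifene-versus-placebo contrast to regain power. Both documents test each dose separately. At one-sided 0.0125 per endpoint, such a contrast would spend a further 2 × 0.0125 = 0.025 outside the Bonferroni scheme, for only about 39-46% power per endpoint.

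The cost is a few lines of SAP text and a less favourable stated figure. No dataset or primary model changes.

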9.3. STATISTICAL METHODOLOGY

An interim analysis is planned when half of the planned evaluable patients has reached the primary endpoints at 7 and 14 days (i.e. assessments available). The intent of the interim analysis is either for identification of early superiority of raloxifene (early efficacy), or for an early stop of one or both treatment arms for futility, or for blind sample size reassessment.

Pocock's spending functions and CP will be used to control the type I and II errors for analyses of primary endpoints. Pocock's boundaries (on standardized Z scale) for efficacy and futility at interim and final analyses are reported in Table 1.

Table 1: Pocock spending functions boundaries for primary endpoints

Analysis	Sample Size	Standardized Z Scaleboundaries for primary endpoints	
		Alpha	Beta
Interim	50%	2.69640	1.59184
Final	100%	2.69640	2.69640

The analysis will be conducted by an independent statistician who will communicate to the Sponsor the result of the interim analysis and the consequent decisions on the continuation of the study, drop of an unefficacious treatment arm and on the reassessment of sample size, if required.

On the basis of Pocock's boundaries and CP at interim analysis, each treatment arm will be classified and ranked as "Effective", "Favorable", "Promising", or "Unfavorable". According to the most effective up-ranked arm, a decisions on the continuation of the study and on the reassessment of sample size will taken.

In case only one treatment arm is defined as "Unfavorable" at the interim analysis, this arm will be dropped from the continuation of study and no additional subjects will allocated to it. Already randomized subjects will continue the follow-up as planned.

Criteria for classification and ranking of treatment arms and possible consequent actions are reported in Table 2.

Table 2: Criteria for classification of treatment arms and actions post-interim analysis

Arm Classification	Criteria		Action based on the most up-ranked treatment arm
	Pocock's Alpha	Higher Conditional Power between Virologic and Clinical endpoint	
1 - Effective	Z > 2.69640	AND CP>90%	Stop for efficacy
2 - Favorable	-	CP>80%	No sample size reassessment
3 - Promising	-	35%<CP≤80%	Sample size reassessment
4 - Unfavorable	Z ≤ 1.59184	OR CP≤35%	Stop for futility

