9.5.2. Analysis of efficacy variables

9.5.2.1. Primary analyses

The proportion of subjects with undetectable SARS-CoV-2 at PCR at day 7 after randomization (virologic endpoint) and the proportion of subjects who not requires supplemental oxygen therapy (NEWS ≤ 2) and/or mechanical ventilation at day 14 after randomization (clinical endpoint) will be separately analyzed by means of logistic regression models adjusting by pre-defined factors as center, age, gender and post-menopausal status. Additional covariates may be defined in the SAP. Each treatment arm will be compared independently with the placebo.

The null hypothesis for the virologic endpoint is that proportion of treated subjects with undetectable SARS-CoV-2 at PCR at day 7 after randomization is lower or equal the placebo one ($\pi_{PLACEBO}$). Two sets of null and alternative hypotheses are provided, one for each treatment dosage:

$$H_{01-60mg}: \pi_{RALOXIFENE-60mg} \leq \pi_{PLACEBO}$$

$$H_{01-120mg}: \pi_{RALOXIFENE-120mg} \leq \pi_{PLACEBO}$$

$$H_{11-60mg}: \pi_{RALOXIFENE-60mg} > \pi_{PLACEBO}$$

$$H_{11-120mg}: \pi_{RALOXIFENE-120mg} > \pi_{PLACEBO}$$

The null hypothesis for the clinical endpoint is that proportion of treated subjects who not requires supplemental oxygen therapy (NEWS ≤ 2) and/or mechanical ventilation at day 14 after randomization is lower or equal the placebo one ($\pi_{PLACEBO}$). Two sets of null and alternative hypotheses are provided, one for each treatment dosage:

$H_{02-60mg}: T_{RALOXIFENE-60mg} \leq \pi_{PLACEBO}$ $H_{02-120mg}: T_{RALOXIFENE-120mg} \leq \pi_{PLACEBO}$ $H_{12-60mg}: T_{RALOXIFENE-60mg} > \pi_{PLACEBO}$ $H_{12-120mg}: T_{RALOXIFENE-120mg} > \pi_{PLACEBO}$

Superiority of raloxifene will be claimed if at least one null hypothesis is rejected, at interim or at final analysis according to criteria shown in section 9.3.

Sensitivity analyses will be defined in the SAP to assess the robustness of results on primary endpoints versus the presence of missing data (unexpected) and the presence of protocol deviations.

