8.4 MULTIPLE COMPARISONS/ MULTIPLICITY

Bonferroni method is used to adjust for multiple endpoints and treatment comparisons.

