14.1.1 PRIMARY EFFICACY ENDPOINTS AND ANALYSES

1. Proportion of patients with undetectable SARS-CoV-2 at PCR at day 7 after randomization (virologic endpoint). This endpoint will be derived as below.
 - Based on Approved molecular test (PCR) result at day 7, the responses will be considered as “detectable” if PCR result is “Positive” otherwise “undetectable” if PCR result is “Negative” (Missing PCR result will be considered as missing in the main analysis).

The response (detectable / undetectable) at day 7 will be analysed using Binary logistic regression model with treatment group and pre-defined baseline factors (center, age, status and their interaction effects with treatment group). Odds ratio

will be computed for comparisons of each active treatment group versus placebo. i.e., raloxifene (60 mg) versus placebo and raloxifene (120 mg) versus placebo.

2. The proportion of patients who does not require supplemental oxygen therapy (NEWS ≤ 2) and mechanical ventilation at day 14 after randomization (clinical endpoint). This endpoint will be derived as below.

- If collected NEWS score > 2 or mechanical ventilation at day 14 result “Yes” then the response will be considered as “Required”. If collected NEWS score ≤ 2 and mechanical ventilation with result “No” then the response will be considered as “Not Required” (if both NEWS score and mechanical ventilation are missing, patient will be considered as missing).

The response (Required/ Not required) at day 14 will be analysed using Binary logistic regression model with treatment group and pre-defined baseline factors (center, age, status, baseline NEWS and their interaction effects with treatment group). Odds ratio will be computed for comparisons of each active treatment group versus placebo. i.e., raloxifene (60 mg) versus placebo; and raloxifene (120 mg) versus placebo.

For both virologic and clinical endpoint, Binary Logistic regression will be performed using PROC GENMOD in SAS® on the observed data only to estimate difference in proportions between each active treatment versus placebo and its corresponding 95% (2-sided) confidence intervals. Exponential transformation will be used to obtain the odds ratio and corresponding 95% confidence interval. P-values will be reported based on the Wald tests from Type III analyses. Bonferroni method will be considered to handle multiple treatment comparisons.

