18 CHANGES FROM PROTOCOL

Following are the changes from the protocol:

- a. Specification of additional populations-All Patient Enrolled (ENR) and Randomized Population (RND).
- b. Text “Subjects”, “Participants” changed to “Patients”.
- c. Baseline characteristics “gender” and “Child-bearing potential status” are combined and derived a new categorical variable with categories Male, Female pre-menopausal status and Female post-menopausal status to be included as factor “Status” in the statistical model of analysis of efficacy endpoints.
- d. Due to the premature interruption of the enrolment, no interim analysis will be done.

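### The interim analysis was cancelled but the final rejection threshold was not re-set: the documents leave Z > 2.696, 2.498 and 2.241 all readable as the rule

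*SAP*

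**What the plan says.** **Protocol.** Section 9.3 states that "Pocock's boundaries (on standardized Z scale) for efficacy and futility at interim and final analyses are reported in Table 1". For efficacy, Table 1 gives 2.69640 at the interim (50% of the sample) and again at the final analysis. Section 9.5.2.1 claims superiority if at least one null hypothesis "is rejected, at interim or at final analysis according to criteria shown in section 9.3". There are four null hypotheses: two endpoints (virologic at day 7, clinical at day 14) by two doses.

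**SAP, design text.** Section 4.1.2 sets the error rate as "controlling the one-sided alpha below 0.025", says that "an interim analysis will take place when 50 patients per arm (N=150) have reached their primary endpoints", and keeps the sentence "Pocock's spending functions and conditional power (CP) will be used to control the type I and II errors".

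**SAP, what changed.** Section 4.3 reports that enrolment stopped with 68 patients included. Section 18(d) records: "Due to the premature interruption of the enrolment, no interim analysis will be done". Section 18 lists no withdrawal or replacement of the protocol boundary.

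**SAP, final analysis.** Section 8.4 says "Bonferroni method is used to adjust for multiple endpoints and treatment comparisons". Section 14.1.1 says "Bonferroni method will be considered to handle multiple treatment comparisons" and does not mention endpoints in that sentence. It reports Wald Type III p-values and 95% two-sided intervals. It declares superiority if any one null hypothesis is rejected, without the protocol's reference to section 9.3 and without a critical value.

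**The concern.** A two-look boundary is higher than a one-look boundary because part of it pays for the interim test. Once that look is cancelled, the final level has to be stated again. It was not, and the remaining texts do not agree with each other.

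The rule for the primary claim is therefore open in both directions. A result with Z between 2.498 and 2.696 succeeds under SAP 8.4 and fails under Protocol Table 1. A result with Z between 2.241 and 2.498 succeeds under a literal reading of SAP 14.1.1 and fails under SAP 8.4. If this is not settled before unblinding, the threshold can be chosen with the results in view.

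**Working it through.** **Inputs.** One-sided 0.025 (SAP 4.1.2); four hypotheses (SAP 14.1.1); interim at half the information (Protocol Table 1); 25% to 50% and 50% to 75% (SAP 4.1.2); 68 patients (SAP 4.3), about 22.7 per arm at 1:1:1. The 23/23/22 split used below is an assumption.

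**Step 1: reproduce the plan's figure.** The level per test is 0.025/4 = 0.00625. For two equally spaced looks with a constant bound c, solve P(Z₁ > c or Z₂ > c) = 0.00625 with correlation √0.5. This gives c = 2.69640, exactly the Table 1 value. So 2.69640 is Bonferroni over four tests plus the price of one interim look.

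**Step 2: use that bound at a single look.** 1 − Φ(2.69640) = 0.003505 per test. Over four tests, 4 × 0.003505 = 0.0140 of 0.025. Unspent share: 1 − 0.003505/0.00625 = 43.9%.

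**Step 3: the three thresholds.**

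| Reading | One-sided level per test | Z | Sum over four tests |
|---|---|---|---|
| Protocol 9.3 carried forward | 0.003505 | 2.696 | 0.0140 |
| SAP 8.4: endpoints and doses | 0.025/4 = 0.00625 | 2.498 | 0.025 |
| SAP 14.1.1 read literally: doses only | 0.025/2 = 0.0125 | 2.241 | 0.05 |

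The sum is an upper bound on the family-wise error. The true rate is somewhat lower because both doses share one placebo arm. The 95% two-sided intervals in 14.1.1 correspond to one-sided 0.025 (Z = 1.960) and match none of the three.

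**Step 4: power for one comparison, pooled z test, n = 22.67 per arm.** Power = Φ[(0.25 − Z × SE₀)/SE₁]. The mean rate is 0.375 (or 0.625), so SE₀ = √(2 × 0.375 × 0.625/22.67) = 0.1438. SE₁ = √((0.1875 + 0.25)/22.67) = 0.1389. Both endpoints give the same values.

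- Z = 2.696: Φ(−0.99) = 16.1%
- Z = 2.498: Φ(−0.79) = 21.6%

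**Step 5: power for at least one of four.** Simulation with 200,000 runs, 23/23/22, complete data, the planned effect in both doses, and latent correlation between a patient's two endpoints from 0.5 to 0:

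| Test | Z > 2.696 | Z > 2.498 | Z > 2.241 |
|---|---|---|---|
| Unadjusted logistic Wald | 37–40% | 46–50% | 61–65% |
| Pooled z | 41–44% | 55–59% | 67–71% |

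One-sided Fisher tests, the SAP's last fallback, give 27–29% at 2.696 and 39–41% at 2.498. The results jump between thresholds because the statistics are discrete at this size.

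**The case against.** The strongest reply is that the SAP governs the final analysis and never prints 2.69640. Its decision rule leaves out the protocol's pointer to section 9.3. The Pocock sentence sits under sample size, and its condition, an interim at half the patients, no longer applies. The SAP's one reference to Protocol 9.3 concerns stopping enrolment at the interim. On this view the Pocock text is only a record of the design, and the operative method is Bonferroni.

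This stands in part. A reader might infer that the final threshold is still fixed at 2.69640 and that 44% of alpha is already lost. The documents do not support that: the loss arises only if the protocol boundary is carried forward. A reader might also infer that carrying it forward threatens type I error. It does not; it is conservative. Nor is Table 1 the only numeric level in the documents, since Protocol 9.5 sets a two-sided 0.05 default for tests not otherwise specified.

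The reply does not close the gap. The protocol ties final rejection to section 9.3, and SAP section 18 does not list that as changed. The Bonferroni wording that would replace it covers endpoints and doses in 8.4 but only doses in 14.1.1. The looser reading no longer guarantees the stated 0.025.

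Two further objections hold. The power figures do not describe the planned model, which adds center, age, status, baseline NEWS (clinical endpoint) and treatment interactions and uses observed data only. And single-comparison power is far below the planned 80% under any of these thresholds, so re-setting the level does not rescue the trial.

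**Conclusion.** The point holds as an undefined decision rule. After the interim was cancelled, the final rejection threshold was not re-set, and the documents support 2.696, 2.498 or 2.241 depending on which section is followed. The first is conservative and leaves 43.9% of alpha unspent if used. The second matches the stated one-sided 0.025 over four tests at one look. The third sums to 0.05, twice the stated level.

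The threshold arithmetic is exact and Table 1 is reproduced. The power differences are illustrative. They rest on a 23/23/22 split, complete data, the planned effects in both doses and unadjusted tests; moving from 2.696 to 2.498 then adds roughly 10 to 15 percentage points to the chance of at least one success.

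**What to change.** Before unblinding:

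- In SAP 8.4 and 14.1.1, state that because no comparative interim look took place, each of the four one-sided hypotheses is tested once at 0.025/4 = 0.00625. This means Z > 2.498, or a two-sided Wald p < 0.0125 with the effect in the favourable direction.
- Report matching two-sided 98.75% intervals (1 − 2 × 0.00625).
- Correct 14.1.1 so that Bonferroni covers both endpoints and both doses, as 8.4 does.
- In 4.1.2, mark the Pocock and conditional-power text as superseded design rather than deleting it. Sections 8.4 and 14.1.1 contain no such text.
- Record the new threshold in section 18.

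The condition is that the sponsor confirms nobody saw unblinded comparative data. The cost is SAP wording only, with no patients or new data; SAP 4.4 already places SAP authorization ahead of unblinding. Holm's step-down procedure would be a valid option at the same family-wise level, but it is a preference and not part of the defect.
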